Appendix V Regional Alopecia Assessment.....	73
Appendix VI Surgical Wound Complication Asessment.....	7

Study Schema

Localized, resectable soft tissue sarcoma of the extremity/limb girdle or superficial trunk

Pre-operative radiation therapy

Dose: 42.75 Gy in 15 fractions

Definitive surgical resection

(3-6 weeks interval between radiation therapy and definitive surgery)

Event Monitoring

List of Abbreviations

AE	Adverse Event/Adverse Experience
BID	Twice daily
cGy	centiGray
CRF	Case Report Form
CT	Computed Tomography
CTCAE	Common Terminology Criteria for Adverse Events
CTV	Clinical Target Volume
DSMB	Data and Safety Monitoring Board
DVH	Dose Volume Histogram
ECOG	Eastern Cooperative Oncology Group
eCRF	Electronic Case Report Form
ER / ES	Electronic Record and Electronic Signature
Gy	Gray
GTV	Gross Tumor Volume
ICRU	International Commission on Radiation Units and Measurements
IMPT	Intensity Modulated Proton Therapy
IMRT	Intensity Modulated Radiotherapy
IND / IDE	Investigational Drugs and Devices
IRB	Institutional Review Board
ITV	Internal Target Volume
LFR5	Local Failure Rate at 5 years
MCCC	Mayo Clinic Cancer Center
MRI	Magnetic Resonance Imaging
PROMISE	Patient-Reported Outcomes Measurement Information System
PS	Performance Status
PTV	Planning Target Volume
RBE	Relative Biological Effectiveness
RT	Radiation Therapy
SOC	System Organ Class
TESS	Toronto Extremity Salvage Score
UPIRTSO	Unanticipated Problems Involving Risks To Subjects or Others
VMAT	Volumetric Modulated Arc Therapy
3DCRT	3D Conformal Radiation Therapy

1.0 Background and Rationale

Approximately 12,000 patients are diagnosed with soft tissue sarcomas annually in the United States, accounting for 1% of all adult malignancies.¹ Given the rarity, diversity (> 60 different histologies), and treatment complexity associated with soft tissue sarcomas, patients routinely undergo treatment at specialty centers. Historically, extremity soft tissue sarcomas were treated with amputation. Advances in radiation therapy and surgical techniques, however, have made radiation therapy plus limb-salvage surgery the standard treatment for most localized, extremity soft tissue sarcomas.²⁻⁵ Superficial trunk soft tissue sarcomas are treated in a similar fashion. With this multi-modal treatment approach, the 5 year local recurrence rate for extremity and superficial trunk soft tissue sarcomas is $\leq 10\%.$ ⁶

Radiation therapy can be administered preoperatively, intraoperatively, postoperatively, or as a combination of the aforementioned.^{2,3,7} Preoperative radiation therapy is associated with a higher acute wound complication rate compared to postoperative radiation therapy.⁶ O'Sullivan et. al. reported a 35% acute wound complication rate with preoperative radiation therapy compared to a 17% rate with postoperative radiation.⁶ Acute wound complication was defined as a major wound issue requiring an invasive intervention (i.e., second surgery or hospitalization for wound care) within 3 months of surgery.⁶ Several other reports document similar acute wound complication rates.⁸⁻¹²

Many centers in the United States and abroad favor pre-operative radiation therapy due to the lower total radiation dose administered (50 Gray (Gy) versus 60-66 Gy) and smaller treatment volume compared to postoperative radiation therapy. These aspects are thought to contribute to the lower irreversible, long-term toxicity rates seen with preoperative radiation therapy.^{13,14} Davis et. al. reported more frequent rates of fibrosis (48.2% versus 31.5%), edema (23.2% versus 15.1%), and joint stiffness (23.2% versus 17.8%) with postoperative radiation therapy compared to preoperative radiation therapy.¹⁴ Higher rates of irreversible, long-term toxicities adversely affect patient function.^{13,14} Lastly, preoperative radiation therapy optimizes the chances of obtaining a margin-negative resection and may decrease the potential for metastatic cell spread at time of surgery.^{6,8,15}

The radiation therapy course for soft tissue sarcomas is certainly long, with total number of fractions ranging from 25 fractions (preoperative treatment) to 33 fractions (postoperative treatment). Given the financial and time commitments associated with the radiation treatment length, there are potential benefits for patients by reducing the number of daily fractions administered. Shorter treatment duration can translate to reduced costs and improved patient experiences due to reduced travel times, decreased time off work and away from family, and lessened financial demands associated with pursuing treatment at a specialty center. Additionally, a shorter radiation course may lead to higher limb preservation rates and improved survival in minority groups as outcomes are known to be inferior in African American and Latino populations compared to the Caucasian population.^{16,17}

One method to shorten radiation treatment length is to administer a hypofractionated treatment course. Hypofractionated radiation therapy administers the total radiation dose

as larger daily doses compared to conventionally fractionated therapy. This effectively reduces the overall treatment duration by weeks. Hypofractionated radiation therapy is proven to be a more convenient and lower cost option for early stage breast and prostate cancers, without compromising oncologic outcomes or increasing the likelihood of treatment-related side effects.¹⁸⁻²⁰ For example, Whelan et. al. demonstrated the efficacy of a hypofractionated postoperative treatment course (42.56 Gy in 16 fractions) for early stage breast cancer compared to conventionally fractionated treatment (50 Gy in 25 fractions).²⁰ At 10 years, the local recurrence rate was 6.7% for conventionally fractionated radiation therapy versus 6.7% for hypofractionated radiation therapy.²⁰ Additionally, there was no difference in overall survival or cosmetic outcomes between the two treatment arms.²⁰

Hypofractionated radiation therapy has been studied to a more limited degree in soft tissue sarcomas. In Poland, a study of hypofractionated preoperative radiation therapy (25 Gy in 5 fractions) was conducted in 272 patients from 2006 to 2011.²¹ This study yielded a higher local failure rate: 19%, with a median follow up of 35 months.²¹ Of note, the biologic effective dose is 34.27 Gy₁₀ with this regimen compared to 43.83 Gy₁₀ with conventional fractionation, suggesting a higher biologic effective dose is needed with hypofractionation to achieve optimal outcomes. Another preoperative hypofractionated study from University of California Los Angeles studied 28 Gy in 8 fractions (biologic effective dose of 32.63 Gy₁₀).²² The local failure rate at 3 years was 11%.²² Again, these results suggest a higher total radiation dose is needed for efficacy when utilizing a hypofractionated radiation treatment course in soft tissue sarcomas.

We propose conducting a single arm, prospective study to evaluate the efficacy and safety of a preoperative hypofractionated course, 42.75 Gy in 15 fractions, for localized, extremity and superficial trunk soft tissue sarcomas. The biologic equivalent dose of this regimen is 45.20 Gy₁₀, similar to 43.83 Gy₁₀ associated with conventionally fractionated 50 Gy in 25 fractions. The primary aim of the study is to determine acute wound complications rates, as defined by O'Sullivan et. al.⁶ Secondary aims will analyze local failure rate, disease-free survival, overall survival, patterns of relapse, late toxicities, and quality of life/patient-reported outcomes. We hypothesize a 15 fraction hypofractionated radiation therapy course will be associated with equivalent short-term toxicity rates and oncologic outcomes as compared to historical standards.

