16.1.1 Primary Endpoint

The primary endpoint of this trial is the proportion of patients who experience major wound complications within 120 days of surgical resection of soft tissue sarcoma of the extremity and superficial trunk following preoperative radiation therapy of 42.75 Gy in 15 fractions. Major wound complication is defined as secondary unplanned operation under general or regional anesthesia for wound repair (e.g., debridement, operative drainage, or secondary wound closure including rotationplasty, free flaps or skin grafts); or wound management without secondary operation including invasive procedures (e.g., aspiration of seroma or readmission for wound care such as intravenous antibiotics or persistent deep packing for 120 days or longer). All patients meeting the eligibility criteria who have signed a consent form and have begun treatment will be evaluable for the primary endpoint.

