16.2 Statistical Design

The non-inferiority one-sample test was utilized from PASS software for this design (Non-Inferiority of One Proportion using the Z-Test with S(P0) in PASS 16.0.4). A sample size of 108 evaluable patients achieves 80% power (1-sided significance level of 10%) to detect a non-inferiority margin of 10%, assuming that any major wound complication rate of 45% or above is inferior as compared to the current standard of care complication rate of 35%.⁶ We hypothesize that the proposed hypofractionated preoperative radiation therapy of 42.75 Gy in 15 fractions is not inferior to the conventional fractionation of 50 Gy in 25 fractions

by showing the complication rate is $< 45\%$ for the proposed treatment (non-inferiority margin of 10%).

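### The plan describes the event behind its 35% benchmark in two ways (3 months in the background, 120 days with a wider list in the endpoint) and uses 35% unadjusted for the 45% limit and the power

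*Combined protocol and SAP*

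**What the plan says.** Section 1.0 (Background and Rationale) cites reference 6 as having "reported a 35% acute wound complication rate with preoperative radiation therapy". It describes that event as a major wound problem that needs invasive treatment, spelled out as "second surgery or hospitalization for wound care) within 3 months of surgery". The last paragraph of the same section says the primary aim is "to determine acute wound complications rates, as defined by" the authors of reference 6, so the trial claims the benchmark's own definition.

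Section 16.1.1 defines the primary endpoint as the proportion with "major wound complications within 120 days of surgical resection", and the estimator in Section 16.3.1.2 uses the same 120 days. Besides unplanned second operations, Sections 11.1 and 16.1.1 count management without an operation, with these examples: "aspiration of seroma or readmission for wound care such as intravenous antibiotics or persistent deep packing for 120 days or longer". Section 11.1 gives no window for counting events.

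Section 16.2 takes "the current standard of care complication rate of 35" (per cent), cited to reference 6, adds a 10-point margin to reach the 45% limit, and powers the trial on a true rate of 35%.

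**The concern.** This is a single-arm non-inferiority design, so the historical rate is the only comparator. The 35% does two jobs: the margin is counted from it, and it is the assumed true rate for power. The test null itself is 45%. Both jobs need the 35% to refer to the same window and the same kinds of event as the trial's endpoint.

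As written, three statements cannot all be right: the 3-month description, the claim that the trial uses that source's definition, and the 120-day endpoint with procedures that need neither a second operation nor admission. Nothing reconciles them, and nothing adjusts 35% for a longer window or wider list. At stake is whether a result against 45% can be read as non-inferior to conventional fractionation by 10 points, as Section 16.2.1 intends.

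**Working it through.** **Descriptions compared**

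| | Section 1.0 | Sections 11.1, 16.1.1, 16.3.1.2 |
|---|---|---|
| Window | 3 months from surgery | 120 days from surgery (none stated in 11.1) |
| Operations | second surgery | unplanned second operation |
| Without operation | hospitalization for wound care | invasive procedures, e.g. seroma aspiration; readmission; deep packing |
| Form of list | closed (i.e.) | open (e.g.) |

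The window differs by about 30 days. Seroma aspiration is the only item clearly outside the Section 1.0 wording. Readmission matches hospitalization, and deep packing can be read as a form of readmission care.

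**Reproducing the plan's figures**

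Inputs from Section 16.2: P0 = 0.45, P1 = 0.35, one-sided alpha 0.10, power 0.80, Z-test with variance at P0.

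n = [(1.2816 × √(0.45 × 0.55) + 0.8416 × √(0.35 × 0.65)) / 0.10]² = [(0.6376 + 0.4014) / 0.10]² = 107.95, so 108.

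Power at 108 = Φ[(0.10 × √108 − 0.6376) / 0.4770] = Φ(0.842) = 80.01%.

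Both match Sections 16.2 and 16.2.4. The test passes with 41 or fewer complications of 108 (38.0%). The exact binomial power at 35% is 77.4%.

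**Illustration if Section 1.0 describes the source correctly**

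The documents give neither a 90-to-120-day event rate nor an aspiration rate, so the added points below are assumed. Suppose the new schedule is no worse than standard, and the trial's definition lifts the common rate from 35% to P, with N = 108 and the limit fixed at 45%.

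Power = Φ[((0.45 − P) × √108 − 0.6376) / √(P(1 − P))].

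| Points added | P | Margin left to 45% | Z-test power | Exact power | N for 80% |
|---|---|---|---|---|---|
| 0 | 35% | 10 | 80.0% | 77.4% | 108 |
| 1 | 36% | 9 | 73% | 70% | 134 |
| 2 | 37% | 8 | 66% | 62% | 171 |
| 3 | 38% | 7 | 57% | 54% | 224 |

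If the benchmark were restated like for like with the 10-point margin kept, for example 40% against 50%, N would be about 111 and power at 108 about 79%. The issue is therefore where the limit sits, and hardly the sample size.

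**The case against.** The strongest reply is that Section 1.0 is a one-sentence background paraphrase. Its last paragraph says the trial uses the source's definition, and Section 16.2 cites the same source for 35%. Sections 11.1 and 16.1.1 may simply restate that definition in full, with the earlier sentence abbreviating it. The 35% would then already fit the endpoint, and the design would stand. Nothing in the documents excludes this, so the point has to be conditional.

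Four stronger readings are tempting, and the documents do not support them:

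- *That the trial is shown to test a broader event against a narrower benchmark.* Only the source could settle this.
- *That the mismatch makes false success more likely.* If Section 1.0 is right, a longer window or wider list can only raise the expected rate or leave it unchanged. That makes 45% harder to beat.
- *That the trial starts from 77% power because of this problem.* The stated 80.01% reproduces on the plan's own test. The gap between 80% and 77% is binomial discreteness, a separate matter.
- *That a schedule equal to the benchmark could fail only because of the mismatch.* With matched definitions it would still fail about 20% of the time. The mismatch would make failure more likely.

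What remains is that the sections disagree on the definition of the sole comparator, and that at least one of them must be changed.

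**Conclusion.** The inconsistency is real and its consequence is conditional. If the background sentence paraphrases the source wrongly, one sentence needs correcting and nothing in the design changes. If it is right, the 45% limit is tighter than the intended 10 points, and a useful schedule is more likely to be rejected. With an assumed 1 to 3 added points, Z-test power falls from 80% to between 73% and 57% (exact binomial 77% to between 70% and 54%). Those figures show sensitivity and are not estimates. They rest on an assumed shift, on equal true rates for the new and standard schedules, and on the 45% limit staying fixed.

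**What to change.** 1. Check in reference 6 which window and which events the 35% refers to.
2. Make both statements in Section 1.0 agree with Sections 11.1, 16.1.1 and 16.2, and give Section 11.1 an event window. In the same edit, clarify the deep-packing item: packing that must last 120 days or more can hardly be completed within a 120-day window.
3. Keep the 120-day primary analysis. Replacing it would be a primary-endpoint amendment and is not needed here.
4. If the source is a 3-month rate, justify 35% and 45% for the 120-day endpoint or restate them. Also prespecify a sensitivity analysis of second surgery or readmission within about 90 days.

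The Appendix VI form already has start and end dates, a two-way classification and a procedure field, so no new data item is required. Readmission is not a separate class, so some free-text procedures would need review. The split would depend on recorded dates, because Section 4.0 schedules wound assessments at 4–8 weeks and then six-monthly, not at 90 or 120 days. The cost is text edits, one extra tabulation and that review.

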2.0 Goals

2.1 Primary Objective

- 2.1.1 To report the major acute wound complication rate associated with hypofractionated preoperative radiation therapy, 42.75 Gy in 15 fractions. See section 11.1 for definition of major acute wound complications.

2.2 Secondary Objectives

- 2.2.1 To report the 5-year local failure rate associated with hypofractionated preoperative radiation therapy, 42.75 Gy in 15 fractions.
- 2.2.2 To report the 5-year disease-free survival rate associated with hypofractionated preoperative radiation therapy, 42.75 Gy in 15 fractions.
- 2.2.3 To report the 5-year overall survival rate associated with hypofractionated preoperative radiation therapy, 42.75 Gy in 15 fractions.
- 2.2.4 To report long-term toxicity rates associated with hypofractionated preoperative radiation therapy, 42.75 Gy in 15 fractions.
- 2.2.5 To describe patterns of relapse associated with hypofractionated preoperative radiation therapy, 42.75 Gy in 15 fractions.
- 2.2.6 To describe patient reported outcomes/quality-of-life outcomes with hypofractionated preoperative radiation therapy, 42.75 Gy in 15 fractions.

3.0 Patient Eligibility

The patient must meet all selection criteria as specified in Section 3.1 and be agreeable to adhere to the follow-up evaluations and schedule. Written informed consent must be obtained from the patient prior to enrollment and prior to any trial-specific evaluations.

3.1 Inclusion Criteria

- 3.1.1 Males and females age \geq 18 years.
- 3.1.2 Newly diagnosed, histological confirmation of soft tissue sarcoma of the extremities (including limb girdle) or superficial trunk that present as either –
- Deemed a candidate for complete macroscopic resection of the primary sarcoma.

OR

- Having had non-oncologic excisional procedure with positive or uncertain resection margins and still be eligible if the evaluating sarcoma surgeon recommends oncologic re-resection of the surgical bed to obtain negative margins after a course of preoperative radiation therapy.
- 3.1.3 No evidence of nodal or distant metastases as determined by clinical examination on any form of imaging.
- 3.1.4 Eastern Cooperative oncology Group (ECOG) Performance Status (PS) ≤ 3 (Appendix I).
- 3.1.5 Life expectancy greater than 6 months.
- 3.1.6 Patients capable of childbearing must agree to use adequate contraception.
- 3.1.7 Ability to complete questionnaire(s) by themselves or with assistance.
- 3.1.8 Ability to provide written informed consent.
- 3.1.9 Willing to return to enrolling institution for follow-up (during the Active Monitoring Phase of the study).

3.2 Exclusion Criteria

- 3.2.1 Previous radiation therapy to the site of the sarcoma or area surrounding it such that it would be encompassed by the radiation field needed to treat the current sarcoma. In other words, treatment on this trial would require re-irradiation of tissues.
- 3.2.2 Patients with nodal or distant metastases.
- 3.2.3 Rhabdomyosarcoma, soft tissue osteosarcoma, soft tissue Ewing sarcoma, and benign histologies.
- 3.2.4 Any of the following:
 - Pregnant women
 - Nursing women
 - Men or women of childbearing potential who are unwilling to employ adequate contraception

4.0 Test Schedule

	Pre-treatment/ Baseline ≤30 days prior to registration	Hypo-fractionated RT 42.75 Gy in 15 fractions	Post-RT Assessment (+/- 5 days)	Pre- Operative Assessment Within 2 weeks of surgery⁹	Post- Operative Assessment 4-8 weeks Post-Surgery^{6,9}	Years 1 & 2 Post-Surgery Assessment Every 6 Months Post-Surgery^{7,8,9} (+/- 8 weeks)	Years 3-5 Post-Surgery Assessment Annually Post- Surgery^{7,8,9} (+/- 8 weeks)
History, physical exam ⁷ , ECOG status	X		X	X		X	X
Pathology review ¹	X				X		
Primary site MRI ² , ⁵	X			X		X	X
PET/CT or CT Chest ⁵ ,	X			X		X	X
Pregnancy test ³	X						
AE Acute Assessment (See section 10.0)	X		X	X			
Hypofractionated RT		X					
CTCAE v5.0 Solicited Late Toxicity Assessment (See section 10.0)	X				X	X	X
Wound Complication Assessment (Appendix VI/Section 11.0)					X	X	
Regional Alopecia Assessment (Appendix V)	X		X	X			
Joint Stiffness Assessment (Appendix IV)	X		X	X		X	X
PROMISE-10 ^a	X			X		X ⁴	
TESS ^b	X			X		X ⁴	

1. Pathology review includes histopathologic diagnosis of soft tissue sarcoma and grade, where applicable.
2. CT is acceptable if MRI is not advisable.
3. For women of childbearing potential only. Must be done ≤7 days prior to beginning radiation treatment. Tubal ligation and IUD in place are exceptions.
4. Obtained at 12, 18, and 24 months.
5. Within 60 days of enrollment
6. Follow Up timepoints may be evaluated outside the anticipated window as deemed appropriate by Stand of Care Radiation Oncology and Orthopedic Surgery follow up schedule
 - a. Patient-Reported Outcomes Measurement Information System
 - b. Toronto Extremity Salvage Score
7. Assessments may be completed by NP/PA in person or by virtual and/or phone visit if patient is unable to return to study site.
8. Per physician discretion
9. If patient develops any type of disease progression or is unwilling to return to the institution, patients will move to yearly survival follow up. No additional assessments will need to be done.

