16.2.2 Sample Size

This study is expected to need to accrue 108 evaluable patients unless the study is closed early for excessive toxicity. We anticipate approximately 10% lost to follow-up due to 120 day endpoint, therefore we anticipate accruing an additional 12 patients to account for ineligibility, cancellation, or other reasons, making the overall sample size of 120 patients.

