16.3.1 Primary Outcome Analysis

16.3.1.1 Definition: The primary endpoint of this trial is the proportion of patients who experience major wound complications within 120 days of surgical resection of soft tissue sarcoma following preoperative radiation therapy. All patients meeting the eligibility criteria who have signed a consent form and have begun treatment will be evaluable for the major wound complication rate.

16.3.1.2 Estimation: The proportion of major wound complications will be estimated by the number of patients who experience the major wound complications within 120 days following surgery divided by the total number of evaluable patients. 95% confidence intervals using normal approximation to binomial wound complication proportion will be calculated.

16.3.1.3 Over Accrual: If more than the target number of patients are accrued, the additional patients will not be used to evaluate the stopping rule or used in any decision making process; however, they will be included in final endpoint estimates and confidence intervals.

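### No required contact establishes day-120 wound status for operated patients who progress or will not return, so primary-endpoint events can go unrecorded in the direction that favours non-inferiority

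*Combined protocol and SAP*

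**What the plan says.** Section 16.1.1 defines the primary endpoint as "the proportion of patients who experience major wound complications within 120 days of surgical resection". Section 16.3.1.2 estimates it as the number of patients with a complication "within 120 days following surgery divided by the total number of evaluable patients". In 16.1.1 and 16.3.1.1, evaluable means eligible, consented and started on treatment; follow-up is not a condition. Section 13.3 declares inevaluable only those who stop radiotherapy for reasons other than toxicity.

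In the test schedule (4.0) the wound assessment is marked in two columns: 4-8 weeks after surgery, and every 6 months (± 8 weeks) in years 1 and 2. The second column carries footnote 8, "Per physician discretion". Both columns, and the pre-operative one, carry footnote 9: "If patient develops any type of disease progression or is unwilling to return to the institution, patients will move to yearly survival follow up", followed by "No additional assessments will need to be done".

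On loss to follow-up, 16.2.2 says "We anticipate approximately 10% lost to follow-up due to 120 day endpoint" and adds 12 patients to the 108 evaluable. Section 16.2.1 bases the decision on the first 108 eligible patients to reach 120 days after treatment.

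**The concern.** The endpoint closes on day 120, but no wound assessment is scheduled on or near that day. Status between the first post-operative visit and day 120 is picked up afterwards, at the 6-month visit. For a patient who has progressed or does not wish to return, that visit is no longer required. If progression is found on the pre-operative scan and the tumour is still resected, neither wound assessment is required.

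Such a patient began treatment and so stays in the denominator under 16.3.1. If no complication form is filed, the patient adds nothing to the numerator. The event is adverse and the claim is non-inferiority, so every missed event moves the result towards success.

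**Working it through.** **1. Calendar.** Six months is about 26.09 weeks. Less 8 weeks, this gives 18.09 weeks, or 18.09 × 7 = 126.6 days, so the window opens at about day 127. Day 120 is week 17.1. The first post-operative visit falls on day 28 to 56, so the stretch from that visit to day 120 lasts 120 − 56 = 64 to 120 − 28 = 92 days and contains no scheduled visit.

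**2. Timing of the decision.** Section 16.2.1 sets the analysis at 120 days after treatment and 16.2.3 at 4 months. Both come before day 127 after surgery. Section 16.3 delays release of results until the last patient has 6 months of follow-up, but it does not delay the decision analysis. The last patients may therefore be analysed before their 6-month visit.

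**3. Other routes of capture.** Section 7.2 says acute wound complications will be recorded, without tying this to a visit. Section 10.4 limits post-radiotherapy reporting to solicited toxicities, and wound complication is on none of the late-toxicity lists. Footnote 7 allows phone or virtual visits for patients who are unable to return; it does not mention those who are unwilling or have progressed.

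**4. The plan's own figures.** Inputs from 16.2: inferior rate 45%, reference rate 35%, one-sided level 10%, power 80%, Z-test with the standard error at P0.

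- n = [(1.2816 × √(0.45 × 0.55) + 0.8416 × √(0.35 × 0.65)) / 0.10]² = 107.95, rounded up to 108. Normal-approximation power at 108 is 80.01%. Both agree with the plan.
- 108 / 0.90 = 120, also as stated.
- Cut-off: 0.45 − 1.2816 × √(0.45 × 0.55 / 108) = 0.3887. The test succeeds with 41 or fewer events in 108 (38.0%).
- Exact binomial probability of 41 or fewer at a true 45%: 8.4%.

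**5. Effect of missed events.** Let m be the share of patients without the later assessment and f the share of their complications that is missed. If missed events count as none, the recorded rate is 0.45 × (1 − m × f). The documents give neither m nor f. Their only figure near m is the 10% loss in 16.2.2, and the 12 patients added there also cover ineligibility, cancellation and other reasons.

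| m (assumed) | f (assumed) | Recorded rate at true 45% | Exact false success |
|---|---|---|---|
| 0 | – | 45.0% | 8.4% |
| 5% | 20% | 44.6% | 10.0% |
| 5% | 50% | 43.9% | 12.7% |
| 10% | 20% | 44.1% | 11.7% |
| 10% | 30% | 43.7% | 13.7% |
| 10% | 50% | 42.8% | 18.2% |

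**6. Denominator.** Sections 16.1.1 and 16.3.1 keep a treated patient whose day-120 status is unknown. Sections 16.2.1 and 16.2.2 count 108 patients who have completed 120 days, with the lost patients on top. No sentence reconciles the two, and none says how unknown status is scored.

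**The case against.** The strongest reply is that the events are hard to miss. They are unplanned operations, invasive procedures, readmissions or prolonged packing, and most leave a dated medical record. Section 7.2 already calls for them to be recorded. The Appendix VI form has start, end and notification dates, so it can be completed at any time. Footnote 6 lets the first visit follow the standard-of-care schedule, and criterion 3.1.9 admits only patients willing to return. Footnote 9 removes the need for assessments; it does not forbid recording a known event. Nor is the visit gap itself a defect, because full 120-day status can be known only at or after day 120.

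Most of this stands, and it rules out several stronger readings that a reader might infer:

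- That complications in these patients *will* be lost. The documents support only that they can be.
- That 53-77% of the window (64 to 92 of 120 days) is unobserved. That is time without a scheduled visit; dated records can cover it.
- That the plan has a rule scoring missing status as no event. It is the literal result of 16.3.1.2, and it conflicts with 16.2.1 and 16.2.2.
- That false success reaches 33.2%. This needs 10% of patients unassessed and every one of their complications missed, including those before the first post-operative visit.
- That the trial cannot report its primary objective. Nothing in the documents shows losses on that scale.

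The reply does not supply a required step that establishes day-120 status once footnote 8 or 9 applies. A general duty to record does not help if nobody has to ask a patient who may be treated elsewhere.

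**Conclusion.** The point holds as a gap in ascertainment together with an unreconciled denominator. Followed as written, the plan can leave day-120 wound status unknown in operated patients who progress, decline to return or are not seen at the physician's discretion. The literal estimator then errs towards non-inferiority.

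The size is uncertain. At 10% unassessed and 20-50% of their complications missed, false success at a true 45% is 11.7-18.2%, against 8.4% with full ascertainment and a nominal 10%. At 5% and 20% it is 10.0%, so with few such patients the effect is small. These figures rest on assumed fractions and on scoring unknown status as no event. The sample size and power are correct and need no change. This should be fixed: it touches the sole primary endpoint and is cheap to repair, but it does not show the trial to be unsound.

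**What to change.** 1. In section 4.0, exempt the Wound Complication Assessment from footnotes 8 and 9 until day-120 status is known.
2. Require one Appendix VI status check at or soon after day 120 for every resected patient, whether or not the patient has progressed or will travel. Phone, virtual visit or record review is enough. Complete it before the decision analysis in 16.2.1.
3. Reconcile 16.1.1 and 16.3.1 with 16.2.1 and 16.2.2 on unknown status. The rule should not depend on whether an event has already been seen. Dropping patients of unknown status unless they have had an event keeps their events and discards their non-events. For example, at a true 35% with 10% unknown and half of their events already seen, the rate becomes (0.9 × 0.35 + 0.1 × 0.35 × 0.5) / (0.9 + 0.1 × 0.35 × 0.5) = 0.3325 / 0.9175 = 36.2%. One workable rule keeps all resected patients and estimates the day-120 cumulative incidence, censoring at last known wound status, with the test stated to match.
4. Add a sensitivity analysis that counts unknown status as an event. It is needed because censoring at progression may not be independent of wound outcome.

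The cost is an amendment to two footnotes and one schedule row, a few sentences in 16.3.1, one call or chart check per patient, and slightly more analysis. No clinic visit or procedure is added. With complete ascertainment the design stays at 108 patients and 80.01% power. For patients already treated, status can still be recovered where records exist.
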